2.5.1.3 Hand-held dynamometry (lower extremity muscle strength)

Change from baseline in lower extremity muscle strength composite score will be analyzed based on the MMRM model, similar to the primary endpoint described in [Section 2.5.1](#). The model will include summary HHD lower extremity score at baseline, baseline FVC (% predicted) and age (as continuous variables), gender (male or female), treatment group, visit, and treatment-by-visit interaction as fixed effects.

As a supportive analysis, change from baseline in % predicted of the summary score for the lower extremity muscle strength will be analyzed based on the MMRM model, similar to the primary endpoint described in [Section 2.5.1](#). The model will include the % predicted of the summary score at baseline, baseline FVC (% predicted), and age (as continuous variables), gender (male or female), treatment group, visit, baseline HHD % predicted score-by-visit interaction and treatment-by-visit interaction as fixed effects. Similar analyses on the % predicted for each muscle group will be conducted.

Since % predicted values are only available for all muscle groups for patients age 6 or older, the analysis on % predicted HHD lower extremity summary will be performed in mITT patients with an age of 6 or older.

Raw score as well as the % predicted scores for each muscle group will also be summarized descriptively by treatment group and study visit.

In order to evaluate quality of observed changes in muscle strength measured with HHD, a sub-group analysis of HHD data will be performed of data confirmed to be collected by same assessor and with the patient in the same position as baseline and Week 49. HHD outcomes will include all muscle groups and UE and LE composites.

2.5.1.4 Quick Motor Function Test

Change from baseline in total score of QMFT will be analyzed based on the MMRM model in mITT, similar to the primary endpoint described in [Section 2.5.1](#). The model will include total score at baseline, baseline FVC (% predicted), age (as continuous variables), gender (male or female), treatment group, visit, and treatment-by-visit interaction as fixed effects.

Each individual item of the QMFT will be summarized descriptively.

2.5.1.5 12-item short form health survey

Change from baseline in PCS and MCS will be analyzed separately based on the MMRM model, similar to the primary endpoint described in [Section 2.5.1](#). The model will include baseline score (PCS or MCS), baseline FVC (% predicted), and age (as continuous variables), gender (male or female), treatment group, visit, and treatment-by-visit interaction as fixed effects. Descriptive summary of change over time and shift from baseline will be performed as well.

The analyses will be conducted based on the mITT patients who are of age ≥ 18 at screening/baseline.

2.5.2 Multiplicity issues

A sequential test strategy for the primary efficacy endpoint and key secondary endpoints will be used to control Type 1 error rate at 5% in a strong sense. Testing will proceed according to the following order and will stop if there is a non-significant comparison:

1. The primary efficacy endpoint of FVC (% predicted) will be tested for NI of avalglucosidase alfa versus alglucosidase alfa first.
2. If NI is demonstrated, the superiority of the avalglucosidase alfa versus alglucosidase alfa in FVC (% predicted) will be tested with the same overall 5% significance level.
3. If the superiority of avalglucosidase alfa versus alglucosidase alfa is demonstrated on the primary efficacy endpoint, the hypothesis testing for the secondary efficacy endpoints will proceed according to the following order:
 - a) Change from baseline to Week 49 in total distance walked in 6MWT (a superiority test with a two-sided alpha of 0.05),

- b) Change from baseline to Week 49 in % predicted of MIP (a superiority test with a two-sided alpha of 0.05),
- c) Change from baseline to Week 49 in % predicted of MEP (a superiority test with a two-sided alpha of 0.05),
- d) Change from baseline to Week 49 in summary score of lower extremity strength by HHD (a superiority test with a two-sided alpha of 0.05).

Analyses of additional secondary endpoints will be considered for supportive purposes.

2.5.3 Sensitivity analyses for the primary efficacy endpoint in PAP

All sensitivity analyses will be performed using the mITT population, unless otherwise specified.

2.5.3.1 Sensitivity analyses to assess the impact of missing data

The primary analysis model of MMRM for FVC (% predicted) change from baseline is based on the assumption that missing data are MAR. To assess this assumption, missing data patterns will first be summarized descriptively by study visit and treatment. Then, the efficacy profile of those patients with missing FVC (% predicted) at each study visit will be presented by treatment group, as well as the reason for missing at the end of follow-up.

Specifically, the following descriptive summaries will be provided:

- Mean (SE) change from baseline by time of dropout (Week 13, 25, 37, 49, or no dropout [or >49 weeks]) within each treatment arm, as well as both treatment groups combined.
- Mean (SE) change from baseline by completion status (completers vs. dropouts) and further by reason for dropout among those patients who dropped within each treatment arm, as well as both treatment groups combined. The categories may be combined or modified based on clinical reason before the study is unblinded.

The following sensitivity analyses using tipping-point method will be conducted to address potential deviation of MAR assumption. The tipping point approach is like a progressive stress-testing to assess how severe departures from MAR must be in order to overturn conclusions from the primary analysis. If implausible departures from MAR in order to change the results from statistically significance to statistically insignificance, the results will be considered to be robust to the departure from MAR assumption. We will then be more confident in the results obtained based on statistical methods with the MAR assumptions in MMRM. Reference-based imputation is not planned since they may bias towards equivalence and thus is not conservative for NI trial. Additional sensitivity analyses may be added as appropriate if the efficacy profile summaries described above suggestive of NMAR.

Missing data will be imputed 1000 times to generate 1000 complete datasets with the SAS Proc MI procedure. Since in general, the missing pattern will not be monotone, a two-step approach will be used and will be performed by treatment group:

- Step 1: Intermittent (non-monotone) missing data will be imputed first based on the missing-at-random (MAR) assumption and a multivariate joint Gaussian imputation

- model using Markov chain Monte Carlo (MCMC) method within each treatment arm,
- Step 2: The remaining, monotone missing data will be imputed using the sequential regression method.

MAR-based imputations for monotone missing data will be generated using sequential regression multiple imputation, where a separate regression model is estimated for imputation of FVC (% predicted) at each time point. Each regression model will include explanatory variables of treatment, baseline FVC (% predicted), age, gender, FVC (% predicted) values at all previous visits.

The model adds a sensitivity parameter, δ , to the imputed values to reflect the difference in mean change from baseline in FVC (% predicted) between patients with missing data and patients with observed data. A sensitivity parameter $\delta_{\text{avalglucosidase alfa}}$ will be introduced to reflect violation of MAR for the avalglucosidase alfa group. The final imputed values for the avalglucosidase alfa group will be the imputed values from previous two steps- $\delta_{\text{avalglucosidase alfa}}$. The imputed values for the alglucosidase alfa will remain the same, ie, the sensitivity parameter for alglucosidase alfa, δ_{aa} , is set to 0. For each given $\delta_{\text{avalglucosidase alfa}}$ value, a MMRM with FVC (% predicted) change from baseline as the outcome variable and the baseline FVC (% predicted), age (both as continuous variables), gender (male or female), treatment group, visit, and treatment by visit interaction as covariates will be fit. The results from the 1000 analyses will be combined using Rubin's formulae and the 95% confidence interval will be constructed. The testing will be repeated over a range of plausible values for $\delta_{\text{avalglucosidase alfa}}$, and the tipping points with which the non-inferiority is not achieved will be identified separately. This analysis will be performed only when the non-inferiority is demonstrated in the primary analysis.

2.5.3.2 Sensitivity analyses with alternative model or different distribution assumption

The following analyses will be performed to address potential deviation from the primary model assumption

1. An analysis of covariance including baseline FVC, age, gender, treatment group as covariates will be performed for the endpoint of change from baseline in FVC % predicted at Week 49. For the patients who are known to start alternative treatment prior to Week 49, the last value prior to initiation of an alternative treatment will be used in the analysis. For other patients who prematurely discontinued prior to Week 49 but with unknown alternative treatment information, their last value prior to dropout will be used in the analysis.
2. A Wilcoxon-Mann-Whitney (WMW) will be performed for change from baseline in FVC (% predicted) at Week 49. Missing FVC (% predicted) at Week 49 will be imputed by baseline or last assessment (within PAP) for the subject, whichever is worse. This analysis will assess the robustness of the results when the normality assumption which underlies the MMRM model is deviated.
3. Change from baseline in FVC (% predicted) will be analyzed with MMRM model including the covariates specified in the primary model (baseline FVC, age, gender, treatment group, visit, and treatment-by-visit interaction as fixed effects).

4. The FVC (% predicted) will be analyzed with a Linear Mixed Effects model which includes fixed effects of age (as continuous variables), gender, treatment, time (in years) and the treatment * time interaction; as well as subject specific random intercept and random slope. The model will be fitted using restricted maximum likelihood estimation with the PROC MIXED procedure in SAS. Comparison between treatment groups will be made by testing and estimating the contrast of the treatment * time interaction in the model. All FVC (% predicted) values from baseline through Week 49 (based on actual assessment date) will be included for this analysis. This analysis model will be appropriate if the FVC (% predicted) over time is approximately linear.

2.5.3.3 Sensitivity analyses with respect to the constancy assumption

It is expected that the 2 populations from LOTS trial and current trial are generally similar. Sensitivity analyses are planned for key prognostic and predictive factors to demonstrate that the results are robust to small imbalances. The constancy assumption requires that the effect of the active comparator of alglucosidase alfa relative to placebo in the current non-inferiority trial is similar to the effect that was observed in the historical LOTS trial. The constancy assumption will be empirically checked by comparing change from baseline of FVC (% predicted) at Week 49 between the current trial and the historical trial. If constancy assumption violation is suspected based on clinical judgement, an exploratory analysis using the covariate-adjustment regression model approach proposed by Nie and Soon (2) will be performed to evaluate the impact of population difference between the historical trial and the current trial on the degree of constancy assumption violation. An ANCOVA model will be fitted to LOTS data to generate a predictive model for the outcome of change from baseline in FVC (% predicted) at Week 49 as a function of the following covariates: treatment, age, gender, race, duration of disease, baseline FVC, baseline 6MWT, respiratory support device use at baseline, and treatment interaction with gender, baseline FVC, respiratory support device use at baseline based on LOTS trial results. If the difference of the estimated relative effect of control over placebo between the current trial population and the historical LOTS trial population exceeds the non-inferiority margin, the constancy assumption may be violated. In this case, covariate-adjustment fixed margin may be performed by using $\alpha_1=0.2$ and $\alpha_2=0.05$ in the approach proposed by Nie and Soon (2) to adjust for population difference. Note that this approach assumes that violation of constancy assumption is caused by known, imbalanced, predictive baseline characteristics. In reality, violation of constancy assumption can also be caused by unknown baseline characteristics or post-baseline characteristics. In that case, the covariate-adjustment may not be able to make correct adjustment.

2.5.3.4 Additional supportive analyses for the primary endpoint

2.5.3.4.1 Responder analysis

A responder analyses based on relative change from baseline in FVC (% predicted) will be performed. Response will be defined as having a relative change from baseline of $\geq 5\%$, 10% or 15% increase from baseline at Week 49 respectively. Patients without Week 49 value will be considered as non-responders.

2.5.3.4.2 *Changes in respiratory support*

Number and percent of patients with new use or increased use of respiratory device (compare to baseline) will be summarized descriptively by treatment group at Week 13, 25, 37 and 49. Time to increased use of respiratory support will be summarized using Kaplan-Meier estimate if sufficient number of patients reported such events during the PAP. Similarly, time to decreased use of respiratory support will be summarized using Kaplan-Meier estimate if sufficient number of patients reported such events during the PAP. Patients without event will be censored at the last visit within PAP.

2.5.3.4.3 *Correlation between FVC (% predicted) change and other efficacy parameters*

Correlation between FVC (% predicted) change, 6MWT change, and other secondary efficacy endpoints plus patient reported outcomes, HHD upper extremity muscle strength, MIP, MEP, as well as safety endpoints such as inhibitory antibody status and peak antibody titer will be explored graphically. Corresponding summary tables will be generated as appropriate.

2.5.4 Subgroup analyses for the primary efficacy endpoint and key secondary efficacy endpoint in PAP

Subgroup analyses for the primary efficacy endpoint of FVC % predicted and key secondary efficacy endpoint 6MWT will be performed. They will include age group (<18 years, ≥ 18 years but <45 years, and ≥ 45 years old), gender, baseline FVC groups (<55%, and $\geq 55\%$), race, and ethnicity. Due to the limited power in these subpopulations, treatment difference within the subgroup will be difficult to interpret. Therefore, the focus of this analysis is on assessment of interaction between subgroup covariate and the treatment. If p-value for the interaction term is less than 0.1, nature of interaction will be explored to determine if it quantitative interaction or qualitative interaction.

The following three MMRM models for the primary efficacy endpoint will be performed:

- MMRM model to include baseline FVC (% predicted, as continuous), age (as continuous), gender, treatment group, visit, treatment-by-gender interaction, and treatment-by-visit interaction as fixed effects. This will be used to assess the gender interaction with the treatment.
- MMRM model to include baseline FVC (% predicted, as continuous), age (<18 years old and ≥ 18 years old), gender, treatment group, visit, treatment-by-age interaction, and treatment-by-visit interaction as fixed effects. This will be used to assess the age interaction with the treatment. The sample size for age <18 maybe too small for this analysis.
- MMRM model to include baseline FVC (% predicted, as continuous), age (as continuous), gender, treatment group, visit, treatment-by-FVC (categorical) interaction, and treatment-by-visit interaction as fixed effects. This will be used to assess the baseline FVC interaction with the treatment.

The same estimation method, covariance matrix and degree of freedom calculation method as that of the primary analysis will be employed here. The p-value for interaction effect will be provided. A two-sided 95% confidence interval within each subgroup for the least-square mean difference between treatment groups will be provided within the framework of these models.

Additional exploratory subgroup analyses will be performed as well, based on baseline covariates such as region (US vs. non-US), baseline use of walking device, baseline 6MWT, duration of disease, use of walking device, use of respiratory support, and ACE genotype. These data will be summarized descriptively by treatment group within the subgroups. The cutoff based on population median will be used for the continuous variables.

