1.1 STUDY DESIGN AND RANDOMIZATION

EFC14028 is a Phase 3, multicenter, multinational, randomized, double-blind study comparing the efficacy and safety of avalglucosidase alfa and alglucosidase alfa (both at 20 mg/kg qow) in treatment-naïve patients with LOPD Ages 3 and above.

Approximately 96 patients will be randomized to receive either avalglucosidase alfa or alglucosidase alfa in a blinded manner. Randomization will be in a 1:1 ratio with stratification factors based on baseline FVC, gender, age (<18 versus ≥ 18), and region (Japan versus Ex-Japan) among patients of age ≥ 18 . Randomization will be performed within each of the following 6 strata:

1. Age <18,
2. Age ≥ 18 , all genders and FVC (% predicted), Japan,
3. Age ≥ 18 , male and FVC (% predicted) <55%, ex-Japan,
4. Age ≥ 18 , female and FVC (% predicted) <55%, ex-Japan,
5. Age ≥ 18 , male and FVC (% predicted) $\geq 55\%$, ex-Japan,
6. Age ≥ 18 , female and FVC (% predicted) $\geq 55\%$, ex-Japan.

The majority of enrolled patients are expected to be ≥ 18 years of age and ex-Japan. For regulatory reasons, patients ≥ 18 years of age from Japan are included as a separate stratum to ensure that at least one such patient is exposed to avalglucosidase alfa. The other strata (age, FVC % predicted, and gender) were chosen to balance the baseline demographics and characteristics of patients thought to influence treatment outcomes in the Phase 3 AGLU02704 (LOTS) study of Myozyme[®]/Lumizyme[®] (alglucosidase alfa). Few patients <18 years of age are expected to be enrolled and so additional strata were not deemed necessary.

If at the end of the recruitment, less than 4 pediatric patients aged 3 to < 18 years are enrolled, up to 2 additional pediatric patients will be enrolled directly in the open-label avalglucosidase alfa long term follow-up phase where they will receive avalglucosidase alfa.

Patients will be observed in a 49 week blinded treatment phase, in which patients will receive an IV infusion of 20 mg/kg avalglucosidase alfa or alglucosidase alfa qow, followed by an open-label treatment extension phase, in which all patients will receive an IV infusion of 20 mg/kg avalglucosidase alfa qow for up to 96 weeks. The 49 week blinded treatment phase will be considered the primary analysis period (PAP).

An extended open-label avalglucosidase alfa long term follow-up period will last up to 144 additional weeks (or up to avalglucosidase alfa approval in the country of the patient,

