All patients	9 months (38 weeks)	3.77	4.74	(2.36, 5.18)
	12 months (52 weeks)	3.64	4.98	(2.14, 5.15)
	18 months (78 weeks)	3.73	5.35	(2.09, 5.37)

Based on all randomized patients from the LOTS study, the difference between alglucosidase alfa and placebo in change of FVC (% predicted) from baseline at Month 12 (52 weeks) was 3.64 with an 80% confidence interval of (2.14-5.15).

A non-inferiority margin of 1.1 was selected for this study with the following rationale

- A NI margin of 1.1 retained approximately 50% of the treatment effect based on lower bound of the 80% confidence interval.
- A recent literature review on the clinical relevance of outcome measures used in LOPD revealed that in 2/3 of the studies in which LOPD patients were treated with alglucosidase alfa, the changes from baseline in % FVC (predicted) were above or within the minimal clinically important difference (MCID) established for another restrictive respiratory disease, IPF, of 2% to 6% (1). The current proposed NI margin of 1.1 is smaller than this reference range.

Although the NI margin was determined based on the LOTS study with FVC % predicted inclusion criterion of 30-80%, a subgroup analysis conducted in LOTS (CSR in-text Table 11-9) suggested that the estimated treatment difference between alglucosidase alfa and placebo (based on last observed data within 18 months) was larger among those patients with baseline FVC (% predicted) $\geq 55\%$, comparing to those patients with baseline FVC (% predicted) $< 55\%$ (4.74% versus 2.25%). Therefore, including a small percent of patients (capped at 15%) with slightly higher baseline FVC (80-85%) in the current study is not expected to compromise the estimated alglucosidase alfa treatment effect, and the proposed NI margin.

1.3.2 Estimated treatment differences between avalglucosidase alfa and alglucosidase alfa on change from baseline in FVC (% predicted upright) at Month 12 (Week 49)

The estimated treatment difference between avalglucosidase alfa and alglucosidase alfa is limited by the following factors:

- Small number of patients treated with avalglucosidase alfa in TDR12857 study, with 6 months post-baseline assessments,
- No randomized comparison data available between avalglucosidase alfa and alglucosidase alfa,
- Difference in inclusion/exclusion criteria between studies TDR12857 and EFC14028.

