
The primary statistical objective is to test the non-inferiority of avalglucosidase alfa versus alglucosidase alfa at two-sided 5% level of significance. The null and alternative hypotheses based on a non-inferiority margin of 1.1 are described as H_{01} and H_{a1} below:

H_{01} : avalglucosidase alfa–alglucosidase alfa \leq -1.1 versus H_{a1} : avalglucosidase alfa–alglucosidase alfa $>$ -1.1

If the lower bound of the two-sided 95% confidence interval for the difference of avalglucosidase alfa-alglucosidase alfa is larger than -1.1, the study will be considered to have met its primary objective and the non-inferiority of avalglucosidase alfa over alglucosidase alfa is established.

After non-inferiority is demonstrated, a test for superiority of avalglucosidase alfa versus alglucosidase alfa will be performed with an overall two-sided 5% level of significance.

The following SAS code will be used for the primary efficacy analysis:

```
ods output Diff = out1
      LSMMeans = out2;
proc mixed data = DATAIN method = reml;
  class TRT VISIT SEX USUBJID;
  model CHG_FVC = BL_FVC SEX AGE TRT VISIT TRT*VISIT/ ddfm = kr;
  repeated VISIT/type = un subject = USUBJID r;
  lsmeans TRT TRT*VISIT/cl diff;
run;
```

where TRT = treatment group, VISIT = (week 13, 25, 37, 49), SEX = (male, female), AGE = age at baseline (continuous), USUBJID = unique patient ID, CHG_FVC is the change from baseline in FVC (% predicted), and BL_FVC is the baseline FVC (% predicted) value.

The same analysis as described above will be performed for the PP population to assess the robustness of the study outcome.

A US FDA-specific exploratory analysis will be conducted using the method described above for those patients in the mITT population 8 years of age or older in order to match the lower age range of patients in the LOTS trial of alglucosidase alfa. This analysis will be used to support US approval.

In the case that both NI and superiority of FVC (% predicted) are demonstrated, a superiority test for 6MWT will be performed with a two-sided alpha of 0.05.

Note that the type I error is controlled for the primary endpoint of FVC (% predicted) in the above testing procedure. Analyses of secondary efficacy endpoints in PAP

The secondary efficacy endpoints for PAP are described in [Section 2.1.3.2](#).

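### The baseline-FVC subgroup model omits the FVC-category main effect, so the default test of its interaction term has 2 df and does not isolate the interaction with treatment

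*SAP*

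**What the plan says.** SAP 2.5.4 lists three MMRM models for the primary endpoint, each meant to test one interaction with treatment.

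- **Gender model.** After baseline FVC and age it lists "gender, treatment group, visit, treatment-by-gender interaction, and treatment-by-visit interaction as fixed effects". Gender is present both as a main effect and in the interaction.
- **Age model.** Age enters as the two-level category (<18, ≥18), together with treatment-by-age. The main effect is again present.
- **Baseline-FVC model.** Baseline FVC enters as a continuous variable with age and gender, then "treatment group, visit, treatment-by-FVC (categorical) interaction, and treatment-by-visit interaction as fixed effects". The category appears only inside the interaction. The stated purpose is: "This will be used to assess the baseline FVC interaction with the treatment".

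The same section makes the interaction the focus of the subgroup work, because treatment differences within subgroups will be hard to interpret with limited power. It adds: "If p-value for the interaction term is less than 0.1, nature of interaction will be explored". On reporting it says: "The p-value for interaction effect will be provided". No contrast, degrees of freedom or code is given for these tests. The estimation method, covariance matrix and degrees-of-freedom method are taken from the primary analysis. The only code in the SAP (2.5.1) begins its factor list with "class TRT VISIT SEX USUBJID", so treatment is a CLASS variable.

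**The concern.** When an interaction term is listed without one of its main effects, its default test absorbs the missing main effect. Here, with treatment in CLASS, treatment-by-FVC-category without FVC category means a separate category effect in each arm. The default null is then that neither arm shows a category effect once a straight line in baseline FVC is fitted. The question the SAP sets is whether the two arms have the same category effect.

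The difference matters if prognosis departs from a straight line near 55% in a way common to both arms. That departure would count as evidence of interaction and could set off the p<0.1 trigger. In the other direction, the second degree of freedom dilutes the test when a real interaction is spread symmetrically over the arms.

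Baseline FVC is likely to be looked at closely. It is one of the stratification factors, which were "chosen to balance the baseline demographics and characteristics of patients thought to influence treatment outcomes" (SAP 1.1). SAP 1.3.1 also reports different alglucosidase alfa effects against placebo above and below 55% when it defends the margin.

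**Working it through.** **Inputs.** SD 5.1, N = 96 allocated 1:1, and 10% missing come from SAP 1.3. The cut at 55% and the 0.1 trigger come from SAP 2.5.4. The four visits and CLASS coding come from SAP 2.5.1. The baseline FVC distribution, prognostic shapes and inter-visit correlations are assumptions, because the documents do not give them.

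**Check of the inputs against the plan.** 96 × 0.9 / 2 = 43.2, so 43 per arm. The noncentrality is (2.0 + 1.1) / (5.1 × √(2/43)) = 3.1 / 1.100 = 2.82. A two-sided 5% t-test on 84 df then has power 79.6%, the Table 4 entry for SD 5.1 and difference 2.0. The SAP gives no figure for the interaction test.

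**Degrees of freedom.** Without the interaction term, the four-visit design has rank 1 (intercept) + 1 (FVC) + 1 (age) + 1 (gender) + 1 (treatment) + 3 (visit) + 3 (treatment-by-visit) = 11.

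- Adding treatment-by-FVC-category as written gives rank 13, so the term has 13 − 11 = 2 df.
- Adding FVC category first gives rank 12, and the interaction then gives 13, so it has 1 df.
- In the gender and age models the interaction has 1 df.

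Write g₀ and g₁ for the category effect in each arm, given linear FVC. The 2-df null is g₀ = g₁ = 0. The interaction null is g₁ − g₀ = 0, and g₁ − g₀ is the difference between the two within-subgroup treatment differences.

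**Same fit either way.** On one simulated single-visit dataset both versions had rank 7 and residual sum of squares 1531.776. The treatment differences were 1.924 (<55%) and 0.693 (≥55%) in both. The 1-df contrast between them was −1.232 (unrounded inputs), F = 0.3623, p = 0.549 from either version. The 2-df test of the term as written gave F = 0.208, p = 0.813.

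**Chance of p<0.1 with no interaction.** Single-visit ANCOVA, n = 86, residual SD 5.1, baseline FVC N(60, 14) truncated to 30–85 (36% below 55), 8,000–10,000 runs per case:

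| Prognosis shared by both arms | 2-df | 1-df |
|---|---|---|
| Linear (step 0) | 9.7% | 9.8% |
| Step of 1 point at 55% | 12.7% | 9.2% |
| Step of 2 points | 21.8% | 9.7% |
| Step of 3 points | 36.1% | 10.1% |
| Gradual sigmoid, total rise about 2 / 4 / 6 points | 10.7 / 12.6 / 17.1% | 10.1 / 10.1 / 9.8% |
| Steep sigmoid, rise about 2 / 3 / 4 / 6 points | 12.7 / 16.4 / 22.7 / 36.5% | 10.0 / 9.5 / 10.1 / 10.1% |
| Slope change at 55% of 1 / 2 points per 10% | 10.7 / 11.3% | 10.6 / 10.2% |

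The sigmoids are A·tanh((FVC − 55)/w) with w = 10 (gradual) or 5 (steep), and the total rise is about 2A. Moving the share below 55% between 25% and 49% left the 2-df figures at 21.5–22.7% for a 2-point step and 34.2–36.3% for a 3-point step.

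**Four-visit version.** Rates come from the noncentral F on each patient's visit mean, assuming complete data and compound symmetry with correlation 0.5–0.9. N was 86–96, and baseline FVC was uniform on 30–85 or N(62, 14) truncated. The 2-df rate was 10% with no step, 14–18% for a 1.25-point step and 26–41% for a 2.5-point step. The 1-df rate was 10% throughout. If treatment and category were both numeric 0/1 and only their product were entered, the test would have 1 df but would still reject 15–22% of the time at a 2.5-point step.

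**Power for a true interaction at p<0.1** (single visit, 10,000 runs). The 2.49-point size is 4.74 − 2.25, the gap in SAP 1.3.1 ("4.74% versus 2.25"). That gap is an effect against placebo and serves only as a scale.

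| Interaction | 2-df | 1-df |
|---|---|---|
| 3 points, all in one arm | 36.3% | 36.3% |
| 3 points, split symmetrically (two runs) | 29.2%, 29.7% | 35.3%, 36.3% |
| 2.49 points, all in one arm | 27.1% | 27.7% |
| 2.49 points, split symmetrically | 22.5% | 28.3% |

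**The case against.** The model is not wrong as a fitted model. With or without the main effect it gives the same fit, the same subgroup differences and the same confidence intervals. The SAP states that the target is the interaction with treatment, and an analyst who follows that purpose can take the 1-df contrast from the fit as written. All of this is true, so the problem lies in one p-value. It does not remove the problem: the SAP promises a p-value for the interaction and names no contrast, and the default test of the term it lists answers another question.

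The second objection is that the large false-trigger rates need a jump in prognosis at 55%, which no document supports. A stratification cut-point is not evidence of a discontinuity, and the figures in SAP 1.3.1 are treatment effects against placebo, not shared prognosis. This stands as a limit on size. With linear prognosis there is no inflation, and with a slope change or gradual sigmoid the rate is 11–17% against a nominal 10%. The rates of 22% and above need an assumed step of 2 points or more, or a sigmoid steep enough to act like one.

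Third, little follows from the trigger. It leads only to exploring the nature of the interaction, using subgroup estimates that are correct. No claim depends on it, since the analysis lies outside the hierarchy in SAP 2.5.2. The power loss is also small: none to speak of for a one-arm interaction, and about 6 points for a symmetric one. These points hold the severity down but do not argue for leaving the text as it is.

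**Conclusion.** The concern holds, at minor severity. The third model in SAP 2.5.4 omits the FVC-category main effect that its two companion models have in their own form. Under the CLASS coding of SAP 2.5.1, the default test of the listed interaction has 2 df and mixes the treatment interaction with any shared departure from linearity at 55%.

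The omission and the degrees of freedom follow from the text and the algebra. The practical size is less certain. It depends on the default test being the one reported, and on a prognostic shape that the documents do not describe. The percentages illustrate assumed distributions and are not predictions for this trial. The primary non-inferiority and superiority tests, the secondary hierarchy, and all subgroup estimates and intervals are unaffected.

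**What to change.** Add FVC category (<55%, ≥55%) as a main effect in the third model, keep continuous baseline FVC, and report the 1-df treatment-by-FVC-category test. Equivalently, leave the model as written and add one sentence stating that the interaction p-value is the 1-df contrast between the two within-subgroup treatment differences at the cut of 55%. Either costs one term or one sentence in one line of the SAP. The fit, the subgroup estimates and their confidence intervals do not change.
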